### 3.8 Endpoint evaluation index

To verify the safety and efficacy of the single-port robot (SPr) in breast conserving surgery, the primary endpoint of this study was the success rate of breast conserving surgery. Successful breast-conserving surgery was determined by a negative tumor margin at least 2-3mm from normal tissue, and secondary endpoints included postoperative pain score and cosmetic score.

#### 3.8.1 Primary endpoint indicators

Success rate of breast conserving surgery under single port robotic transaxillary approach.

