## Scenario summary

research topic	Application of Single-Port Robot-Assisted Breast-Conserving Surgery via Axillary Approach for Breast Cancer.
Main purpose of the study	
1. To evaluate the efficacy of single-port robots in breast cancer breast conserving surgery. Including differences in operative time and intraoperative number of lymph nodes detected.
 
2. To evaluate surgical safety: the incidence of surgical transfer and the incidence of postoperative complications.

Secondary purpose of the study	Pain and cosmetic scores of patients after breast conserving surgery under a single port robotic approach.
research design	
 Randomized controlled trial
 
 non-randomized controlled study
 
 Single-arm study
 
 Other
 
 Single-center study    multicenter study
 
Whether blind:  yes  no

subject investigated	Patients undergoing breast-conserving surgery for breast cancer.
intervention study	Single-port Robot-assisted breast-conserving surgery for breast cancer.
endpoint criteria	Success rate of breast conservation surgery under single-port robotic approach
sample capacity	Total number of cases: 100; 20 in the test group; 80 in the control group

statistical analysis	Double data entry was carried out using Excel 2010, and data analysis was performed with SPSS 25.0. The normality of continuous variables and homogeneity of variance were examined by Kolmogorov-Smirnov test and analysis of variance test respectively. For continuous variables that conformed to normal distribution and had homogeneity of variance, the independent-samples t-test was adopted. For continuous variables that did not conform to normal distribution, the Mann Whitney U test was used. For categorical variables and count data, Fisher's exact test and Pearson chi square test were employed.
Study cycle	November 2024-December 2025

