### 3.3.3 Exit criteria

- 1) Those who cannot complete the single-port robot breast conserving surgery and need to be converted into traditional breast conserving surgery or endoscopic breast preservation surgery.
- 2) The patient voluntarily requests to withdraw from the investigator.
- 3) The patient is associated with other non-tumor conditions so that they cannot continue to accept the study program;
- 4) After inclusion in the study, the investigator cannot be completed due to other reasons.

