#### 4.3 Preliminary analysis

Two-person data entry was performed using Excel 2010 and SPSS 25.0 data analysis. Baseline numerical data will be described as mean, standard deviation or median and interquartile range, and baseline categorical data will be shown as percentage. Normality and homogeneity of variance of continuous variables were tested by Kolmogorov-Smirnov test and ANA variance, respectively. Independent sample t-test for continuous variables meeting normal distribution and homogeneity of variance, Mann Whitney U test for continuous variables not meeting normal distribution, and Fishers exact test and Pearson chi square test for categorical variables and count data. Primary endpoint analysis: The success rate of breast conservation surgery under single hole robot will be compared by Chi-square test (Chi-square test) with exact test if necessary. Use multiple interpolation methods to deal with missing data. Postoperative cosmetic score and postoperative pain score were calculated and analyzed according to the standard scale.

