#### 4.4 Effectiveness analysis

The primary endpoint of this study is the success rate of breast-conserving surgery in patients with breast cancer. The success of breast-conserving surgery was determined by a negative tumor margin at least 2-3mm from normal tissue. Secondary endpoints included surgical specimen quality, functional outcome, and quality of life (postoperative pain score, postoperative cosmetic score).

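### The primary endpoint is worded with and without a robotic condition, and no rule says whether a converted patient with a clear margin is a success, a non-success or removed

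*SAP*

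**What the plan says.** The endpoint is worded in two ways.

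- **No condition on technique.** Section 3.8 states that "the primary endpoint of this study was the success rate of breast conserving surgery" and gives the criterion: "Successful breast-conserving surgery was determined by a negative tumor margin at least 2-3mm from normal tissue". Section 4.4 repeats both: "The primary endpoint of this study is the success rate of breast-conserving surgery in patients with breast cancer", judged by the same margin.
- **Tied to the robot.** Section 3.8.1, which formally lists the primary endpoint, reads "Success rate of breast conserving surgery under single port robotic transaxillary approach". The summary reads "Success rate of breast conservation surgery under single-port robotic approach". The only sentence that specifies the primary test, in 4.3, reads "The success rate of breast conservation surgery under single hole robot will be compared by Chi-square test", with an exact test if necessary.

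Three other places bear on conversion. Exit criterion 1 in 3.3.3 covers "Those who cannot complete the single-port robot breast conserving surgery and need to be converted into traditional breast conserving surgery" (or into endoscopic surgery). The summary lists "the incidence of surgical transfer and the incidence of postoperative complications" under surgical safety. Section 3.5(3) describes when a robotic operation is converted. Section 4.2 is headed as the analysis population but defines no analysis set. The summary describes the study as non-randomised and not blinded.

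**The concern.** The plan expects conversions, because it describes them, counts them and lists them as a reason to exit. It does not say how a converted patient enters the primary endpoint. Under 3.8 and 4.4 a clear margin is a success however the operation was finished. Under the robot-tied wording it is arguable whether a margin cleared after conversion was achieved by the robotic approach. Under exit criterion 1 the patient may not be in the analysis at all.

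The choice could be made after conversions and margins are known, by people who know the groups. Only the robotic arm can contain such patients, so the choice moves one side of the comparison. It also mixes two questions: whether the tumour was cleared, which can be compared across groups, and whether the robot could finish the operation, which exists in one group only. If robotic patients were scored on both and controls on the margin alone, the test would compare different endpoints. Read literally, the test sentence in 4.3 compares a robot-only rate that has no control counterpart.

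**Working it through.** **Inputs from the plan.** Robotic group: 20. Control group: 80 in the summary, 60 in 4.1; that discrepancy is a separate matter, so both sizes are used. The plan gives no conversion rate, expected success rate, significance level or power, so it has no figure of its own to reproduce here.

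**Assumptions.** All 20 robotic patients have clear margins; k of them are converted; control success is varied. Tests are two-sided Fisher exact tests.

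**Step 1: robotic rate under each rule.**

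- Converted counted as success: 20/20 for any k.
- Converted counted as non-success: (20 − k)/20, a loss of 1/20 = 5 points per conversion.
- Converted removed: (20 − k)/(20 − k).

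| k | success | non-success (exact 95% CI) | removed |
|---|---|---|---|
| 1 | 20/20 = 100% | 19/20 = 95% (75.1 to 99.9) | 19/19 |
| 2 | 20/20 = 100% | 18/20 = 90% (68.3 to 98.8) | 18/18 |
| 3 | 20/20 = 100% | 17/20 = 85% (62.1 to 96.8) | 17/17 |
| 4 | 20/20 = 100% | 16/20 = 80% (56.3 to 94.3) | 16/16 |

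**Step 2: effect on the test with k = 3.**

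| Controls | 20/20 | 17/20 | 17/17 |
|---|---|---|---|
| 57/60 | 0.57 | 0.16 | 1.00 |
| 58/60 | 1.00 | 0.097 | 1.00 |
| 59/60 | 1.00 | 0.046 | 1.00 |
| 76/80 | 0.58 | 0.14 | 1.00 |
| 78/80 | 1.00 | 0.053 | 1.00 |
| 79/80 | 1.00 | 0.025 | 1.00 |

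**Step 3: other numbers of conversions, counted as non-successes.**

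- k = 1 never gives p below 0.05; the smallest value is 0.20 (against 80/80).
- k = 2 gives 0.15 against 59/60, 0.10 against 79/80 and 0.038 against 80/80.
- k = 4 gives 0.062 against 57/60 and 0.049 against 76/80.

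**Step 4: how likely conversions are.** With an assumed conversion rate p, P(at least one) = 1 − (1 − p)^20. For p = 5%, 10% and 15% this is 64%, 88% and 96%. The binomial chance of at least three is 8%, 32% and 60%.

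**The case against.** The strongest reply is that the plan contains one success criterion, the margin, stated in the same terms in 3.8 and 4.4. Section 3.8.1 is a one-line entry beneath 3.8 with no criterion of its own, so it most naturally borrows the margin. The summary line is likewise a label. Sections 4.1 and 4.2 state a comparison with the traditional group, so controls can be scored on the margin. Conversion already has its own safety outcome, which supports a margin-only reading.

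Much of this stands. A reader might infer that the plan flatly contradicts itself, that controls have no endpoint, or that the robotic endpoint is a composite of clear margin and robotic completion. The documents do not support these readings: the composite is written nowhere and rests only on the word *under*, and controls have a usable margin criterion through 3.8 and 4.4.

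The reply does not settle how a converted patient is counted. The robot-tied wording appears three times, including in the test sentence, so it is not an isolated slip. Exit criterion 1 adds removal as a third possibility, and 4.2 does not close it.

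It is also fair to say that the test result often does not turn on this. At 95% control success, three conversions scored as non-successes stay above 0.05 with either control size.

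**Conclusion.** The point holds as an unresolved definition: the primary endpoint lacks one wording that fits both groups, and the status of a converted patient is open between success, non-success and removal. The firm part of the size is 5 points on the robotic rate per converted clear-margin patient, success against non-success; removal leaves the rate at 100% when every margin is clear but shrinks the denominator. The effect on significance is conditional. With three conversions it appears only when control success is very high (59/60 or 79/80 among the cases shown), and one conversion never produces it. A reader might conclude that the choice decides the trial; that does not follow, since every conversion and control rate here is assumed. With no conversions the three rules agree. The change should be made because it is cheap and removes an after-the-fact choice that affects one arm.

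**What to change.** 1. Use one primary definition in the summary, 3.8, 3.8.1, 4.3 and 4.4: the proportion of patients meeting the margin criterion among all patients in whom the planned operation was started, applied identically in both groups. Delete the robot-tied qualifier from the endpoint and from the test sentence.
2. State in 4.2 that converted patients stay in the robotic group for analysis and are scored on the margin.
3. Reconcile exit criterion 1 (3.3.3) and exclusion criterion 4 (3.3.2, which turns on margin status after re-resection) with this, so that neither removes a patient from the primary denominator. This concerns analysis membership only, not the surgical decision to convert.
4. Report margin success without conversion for the robotic arm only, with an exact 95% confidence interval and no test against controls, beside the incidence of conversion already listed in the summary.

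The cost is wording in five endpoint places, a statement in 4.2, two criteria to reconcile and one extra descriptive proportion. It adds no patients; margins and conversions of patients who would otherwise exit must be kept. The small downside is that conversion no longer lowers the primary rate, which is why the robot-only measure is reported beside it.

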#### 3.8.2 Secondary endpoint indicators

Measurement of postoperative pain score and postoperative cosmetic score according to the scale (measured time after patient discharge).

### 4. Statistical analysis plan

#### 4.1 Sample size estimation

This study belongs to the phase II clinical study, SPr-breast conserving surgery group enrolled 20 patients, and compared with the tradition-breast conserving surgery group (60 cases), aims to evaluate the single-port robot assisted axillary breast protection in the treatment of breast cancer, later further expand the sample size according to the situation, to compare the clinical efficacy of the two methods.

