## 10. Research progress

November 2024- -June 2025: screen the enrolled patients and complete the preliminary preparation of the project

July 2025-October 2025: Patient data are collected and processed

November 2025- -December 2025: Write the result report

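### The planned control group is 80 (total 100) in the SAP's summary but 60 (implied total 80) in section 4.1, and nothing in the document reconciles the two.

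*SAP*

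**What the plan says.** In the SAP's Scenario summary, the sample capacity entry reads "Total number of cases: 100; 20 in the test group; 80 in the control group".

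Section 4.1 (Sample size estimation) has the same robot group, "SPr-breast conserving surgery group enrolled 20 patients", but a different comparator: "compared with the tradition-breast conserving surgery group (60 cases"). It states no total of its own and gives no success rates, significance level, power, margin or dropout. It then says the study will "later further expand the sample size according to the situation, to compare the clinical efficacy of the two methods", without a number, a group or a time.

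The control group enters the primary analysis in section 4.3, where the success rate "will be compared by Chi-square test (Chi-square test) with exact test if necessary".

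Section 10 (Research progress) runs from screening and preparation (November 2024 to June 2025), through the stage "July 2025-October 2025: Patient data are collected and processed", to the report in November and December 2025. It contains no expansion stage.

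**The concern.** The two statements describe the control group of one study, in current text, and differ by 20 patients. This is not a detail left to a protocol that is not at hand: the SAP states the number twice, once in its own sample size section, and no other document could make both true.

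What is at stake is mainly the reporting of planned against actual enrolment. The study is non-randomised and unblinded, and the choice of operation rests on patient preference, finances and equipment availability. A control number stated in advance is therefore one of the few limits on when control accrual ends. With two numbers in force, stopping at 60 and stopping at 80 can each be called the plan, and the planned ratio is either 1:3 or 1:4.

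**Working it through.** **1. Inputs from the SAP**

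| Source | Robot | Control | Total | Ratio |
|---|---|---|---|---|
| Scenario summary | 20 | 80 | 100 (stated) | 1:4 |
| Section 4.1 | 20 | 60 | 80 (implied) | 1:3 |

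**2. Reproducing the stated total.** Summary: 20 + 80 = 100, so the entry is consistent with itself. Section 4.1: 20 + 60 = 80, which is not 100. The gap is 80 − 60 = 20 controls, or 20/80 = 25% of the larger control group and 20/100 = 20% of the larger total.

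**3. Could dropout explain it?** Inflating 60 by 60/(1 − d) gives 64, 67, 71, 75 and 80 for d = 5%, 10%, 15%, 20% and 25% (rounded up). Only 25% reaches 80. The SAP states no dropout allowance, and the same 25% would raise the robot group to 20/0.75 = 26.7, that is 27. It stays at 20.

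**4. Could a sample size formula settle it?** No. Section 4.1 supplies none of the inputs that such a formula needs.

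**5. Effect on precision.** The success rates below are assumptions; the SAP gives none.

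With a common success rate p, the standard error of the difference is √[p(1 − p)(1/20 + 1/n)]. The ratio for 80 against 60 controls does not depend on p:

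√[(1/20 + 1/80)/(1/20 + 1/60)] = 0.2500/0.2582 = 0.968, that is 3.2% smaller with 80.

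The 95% half-width, 1.96 × standard error, in percentage points:

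| Assumed p | 60 controls | 80 controls | Gain |
|---|---|---|---|
| 80% | 20.24 | 19.60 | 0.64 |
| 90% | 15.18 | 14.70 | 0.48 |
| 95% | 11.03 | 10.68 | 0.35 |

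With unequal rates, the standard error is √[p_r(1 − p_r)/20 + p_c(1 − p_c)/n]. The ratio for 80 against 60 controls is:

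- robot 80%, control 95%: 0.989
- robot 70%, control 90%: 0.984
- robot 90%, control 70%: 0.944
- robot 95%, control 80%: 0.932

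For these four pairs the reduction is 1.1% to 6.8%. They are examples and not bounds.

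**6. Power.** No general statement is possible. For Fisher's exact test (two-sided 5%, full enumeration), power goes from 0.500 with 60 controls to 0.553 with 80 at robot 70%, control 90%. At robot 90%, control 70%, it goes from 0.397 to 0.380. Even the sign of the change depends on the assumed rates.

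**The case against.** The best reconciliation is to read 60 as the initial control group and 80 as the size after the expansion in section 4.1. This does not stand. The expansion sentence names no number, group or date, the summary gives 100 as the total for this study, and section 10 has no stage in which an expansion could occur.

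The second objection is that little follows from the discrepancy. This is largely right. The robot group is 20 in both places and dominates the variance, no derived figure uses either control number, and no test or endpoint definition changes. Sections 3.8 and 3.8.1 also describe the primary endpoint as a success rate under the robotic approach, and its one-group estimate does not involve the controls. But section 4.3 says that rate will be compared, so a control number is needed. The objection limits the seriousness of the point without removing it.

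Third, the expansion sentence is an ambiguity and not an error. A separate later stage is its natural reading, since the schedule has no room for one within this study. That is accepted, and the point on expansion is secondary.

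**Conclusion.** The contradiction is certain and rests on the SAP's own figures: 80 against 60 controls, and 100 against 80 patients in total. The document does not show which was intended. It should be corrected because a planned sample size is a figure against which the trial will be reported, and a 25% shortfall cannot at present be told from completion.

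The numerical consequence is modest. Under assumed common success rates of 80% to 95%, the half-width for the difference changes by about 0.3 to 0.6 percentage points. No claim is made about power.

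**What to change.** State one control number and the matching total in both the Scenario summary and section 4.1: either 80 controls and 100 patients, or 60 controls and 80 patients. The sponsor must choose.

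As a secondary clarification, add a sentence to section 4.1 along these lines: *The primary comparison in section 4.3 is performed once, at this size; any later expansion is a separate stage and is not pooled into this test.* If expansion within this study is intended, section 4.1 should instead specify its size, its timing and how the significance level is adjusted.

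The cost is wording in two places and one added sentence. Choosing 60 adds no patients. Choosing 80 means 20 more controls than section 4.1 plans, but the summary already counts them.

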#### 4.2 Statistical analysis of the population

This study, conducted only in the Army Characteristic Medical Center, is a single-center, prospective clinical cohort study designed to evaluate the safety and efficacy of single-port robots in breast cancer surgery by comparison with the traditional breast-conserving surgery group. During the trial, the clinical data will be

reviewed centrally to ensure uniform quality.

#### 4.3 Preliminary analysis

Two-person data entry was performed using Excel 2010 and SPSS 25.0 data analysis. Baseline numerical data will be described as mean, standard deviation or median and interquartile range, and baseline categorical data will be shown as percentage. Normality and homogeneity of variance of continuous variables were tested by Kolmogorov-Smirnov test and ANA variance, respectively. Independent sample t-test for continuous variables meeting normal distribution and homogeneity of variance, Mann Whitney U test for continuous variables not meeting normal distribution, and Fishers exact test and Pearson chi square test for categorical variables and count data. Primary endpoint analysis: The success rate of breast conservation surgery under single hole robot will be compared by Chi-square test (Chi-square test) with exact test if necessary. Use multiple interpolation methods to deal with missing data. Postoperative cosmetic score and postoperative pain score were calculated and analyzed according to the standard scale.

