## 7.Quality control

(1) Conduct comprehensive training for all participating personnel (including researchers, research nurses, data entry staff, etc.). For example, for the researcher, the inclusion criteria, exclusion criteria, and the specific operation procedures of the intervention measures should be explained in detail.

(2) The personnel participating in the clinical trial should have the corresponding professional expertise, qualification and scientific research ability, and must carefully study and discuss the clinical research plan and trial manual, and be determined after the qualification examination, and the personnel are relatively fixed. Archives management, use of drugs or devices, and correction of relevant testing instruments shall be managed by qualified personnel. Through clinical trial training to make research personnel for clinical trial scheme and its index specific connotation fully understand and understanding, for the description of conscious symptoms should be objective, do not induce or prompt: for the objective indicators shall be specified by the time, place and method of inspection, should pay attention to observe adverse reactions, and tracking.

(3) In order to eliminate the skill differences of surgeons and the potential impact

of surgeon learning curve on the results, only single-port or multi-channel robotic surgical patients with two senior physicians in our department were selected for comparative analysis. Both surgeons have completed more than 30 cases of robotic surgery and have passed the learning curve of robotic surgery.

(4) Standardized implementation of interventions

Establish the intervention implementation record system, detailed record of the time of each intervention, executor, patient response and other information. This traces the implementation of the intervention to facilitate problem detection and quality control.

(5) Normalization of follow-up

Develop a perfect follow-up plan, and clarify the follow-up time point, follow-up content and follow-up method. Follow-up personnel were trained to ensure accurate follow-up data collection.

A follow-up reminder system was established to remind patients to follow up on time through SMS and telephone calls, so as to improve the follow-up rate and ensure the integrity of the study data.

(6) Regular internal quality inspection:

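### The equal-variance check is assigned to analysis of variance, which compares means, and normal data with unequal variances are left without a test; operative time, a main study purpose, falls under this rule.

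*SAP*

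**What the plan says.** The rule for continuous variables appears twice. Section 4.3 (Preliminary analysis) gives the checks: "Normality and homogeneity of variance of continuous variables were tested by Kolmogorov-Smirnov test and ANA variance, respectively". The Scenario summary, in its statistical analysis row, spells the second check out in full: the two properties were "examined by Kolmogorov-Smirnov test and analysis of variance test respectively".

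Section 4.3 then assigns the tests: "Independent sample t-test for continuous variables meeting normal distribution and homogeneity of variance, Mann Whitney U test for continuous variables not meeting normal distribution". The Scenario summary has the same two branches. No Welch or other unequal-variance method appears anywhere in the document.

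Under the main purpose, the Scenario summary describes efficacy as "Including differences in operative time and intraoperative number of lymph nodes detected". The arm sizes are "20 in the test group; 80 in the control group" in the Scenario summary, while section 4.1 has 20 robotic patients "compared with the tradition-breast conserving surgery group (60 cases").

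**The concern.** There are two separate defects.

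- **Wrong check.** Analysis of variance tests whether means differ. With two groups it is the pooled t-test in another form, so the stated variance check is the comparison it is meant to license.
- **Missing branch.** Two properties are checked, but only two of the outcomes have a test: normal with equal variances, and non-normal. Normal with unequal variances has none.

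Operative time is continuous and is named as a main purpose, so the rule governs it. Blood loss and length of stay come under it too where they are analysed. If variances differ, the analyst must either choose a test after seeing the data or use a pooled t-test whose error rate is off. Arms of 20 vs 60 or 20 vs 80 make the second course worse: the pooled standard error is dominated by the larger arm, while the true standard error is driven by the smaller one.

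The document does not settle whether the rule also covers lymph-node number (possibly count data) or the pain and cosmetic scores (analysed according to their scales). Nothing here relies on them.

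**Working it through.** **Inputs.** Arm sizes are 20 vs 60 (section 4.1) and 20 vs 80 (Scenario summary). The plan gives no alpha, SD or effect size for a continuous outcome, so there is no planned figure to reproduce. Assumed: normal data, two-sided alpha 0.05, and robot-to-control SD ratios shown as a range. Paired figures below are for 60 / 80 controls.

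**Step 1: the check read literally.** In simulated two-group data, one-way ANOVA and pooled t-test p-values agreed to within 1e-15. With both at 0.05, a variable passes the check only when p is at least 0.05, so the t-test that follows can never be significant. With equal SDs and a true difference in means:

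| Mean shift (SD) | ANOVA rejects | Levene rejects |
|---|---|---|
| 0.5 | 49% / 51% | 4.8% / 5.5% |
| 0.8 | 86% / 90% | 4.9% / 5.7% |
| 1.0 | 97% / 98% | 5.4% / 5.2% |

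A real difference in means would be recorded as unequal variances. Conversely, with equal means and an SD ratio of 2, ANOVA flags only 16% / 18% of samples, against 94% / 94% for Levene's test (3,000 replicates per setting).

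**Step 2: the check read as a real variance test.** The table takes Levene's test (mean-centred, 0.05) as the intended check, with 200,000 simulations per SD ratio and equal means.

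| SD ratio | Levene fails: no test assigned | Pooled t error among samples that pass | Pooled t error, no check | Levene, then pooled or Welch |
|---|---|---|---|---|
| 0.5 | 91% / 93% | 1.1% / 0.7% | 0.8% / 0.5% | not given |
| 1 | 5% / 5% | 5.0% / 5.1% | 5.0% / 5.1% | 5.1% / 5.2% |
| 1.25 | 22% / 23% | 8.0% / 8.5% | not given | 6.8% / 7.1% |
| 1.5 | 55% / 58% | 11.6% / 13.0% | 10.7% / 12.1% | 7.0% / 7.3% |
| 2 | 93% / 94% | 20.2% / 22.3% | 15.3% / 18.2% | 5.6% / 5.6% |

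Welch's t-test with no pre-test gives 4.9% to 5.1% throughout.

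**Step 3: formula check of the unchecked pooled t-test.** In large samples the type I error is 2 × [1 − Φ(1.96 × SE_pooled / SE_true)]. At SD ratio 2 with control SD 1:

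- 20 vs 60: pooled variance = (19 × 4 + 59) / 78 = 1.731. SE_pooled = √[1.731 × (1/20 + 1/60)] = 0.340. SE_true = √(4/20 + 1/60) = 0.465. Error = 15.3%.
- 20 vs 80: pooled variance = (19 × 4 + 79) / 98 = 1.582. SE_pooled = √[1.582 × (1/20 + 1/80)] = 0.314. SE_true = √(4/20 + 1/80) = 0.461. Error = 18.1%.

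Both agree with the simulation. A separate run of 40,000 replicates gave 10.6% / 12.5% at ratio 1.5 and 15.4% / 18.0% at ratio 2.

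**Step 4: Mann-Whitney U as a fallback.** Sending normal data with unequal variances to Mann-Whitney U does not solve the problem: its type I error is 9.8% / 11.7% at SD ratio 2 (4,000 replicates).

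**The case against.** The strongest reply concerns weight.

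- **Translation.** The wording in section 4.3 is garbled, and the document has other translation slips, so a proper variance test may have been meant. That is plausible. But the Scenario summary names analysis of variance in full, and the missing branch remains under any reading.
- **Not a listed endpoint.** Operative time is under the main purpose but is not among the primary or secondary endpoints in sections 3.8 and 4.4, and the primary endpoint is binary. This stands and limits the consequence.
- **The gap may not arise.** If operative time is non-normal, Mann-Whitney U applies. No SD is given, and section 7 says of the surgeons: "Both surgeons have completed more than 30 cases of robotic surgery and have passed the learning curve of robotic surgery". A larger SD in the robotic arm is therefore only a possibility. This stands too.
- **The largest figures need context.** The 20.2% / 22.3% at SD ratio 2 applies only to the 7.5% / 5.9% of samples that pass Levene's test. As a share of all samples, that is 0.075 × 20.2% = 1.5% and 0.059 × 22.3% = 1.3%. At ratio 1.5 the same product is 0.454 × 11.6% = 5.3% and 0.422 × 13.0% = 5.5%. The ungated pooled figures apply only if the analyst ignores the plan's equal-variance condition. If Welch's test were used in the empty branch, overall error would peak near 7.3% over ratios 1 to 2. All this is correct, but the plan does not name Welch, so that outcome depends on a choice it leaves open.
- **The remedy keeps a normality pre-test.** Data-driven choice is reduced, not removed. This is fair.

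**Conclusion.** The concern holds. Both statements of the rule assign the variance check to a test of means, and both leave normal data with unequal variances without a test. Nothing elsewhere in the document repairs this.

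The textual defect is certain. Its numerical effect depends on assumed normality, an assumed alpha of 0.05 and unknown SD ratios. If the SDs are equal, the pooled t-test holds its level. At a ratio of 1.5, more than half of samples would have no assigned test under a Levene check, and a pooled t-test used regardless would roughly double the nominal error rate. If the robotic arm has the smaller SD, the pooled test is instead conservative (0.8% / 0.5% at a ratio of 0.5).

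The rule should be corrected because it governs a comparison named as a main purpose. It does not touch the primary endpoint.

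**What to change.** In section 4.3 and in the statistical analysis row of the Scenario summary, delete the analysis-of-variance check. Prespecify Welch's unequal-variance t-test, with the mean difference and its 95% confidence interval, for approximately normal continuous outcomes. Keep Mann-Whitney U for non-normal ones.

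A minimum repair is to name Levene's test and assign Welch's test when it fails. That closes the gap but is less good: overall type I error is 6.8% / 7.1% at SD ratio 1.25 and 7.0% / 7.3% at 1.5, against about 5% for Welch without a pre-test.

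The cost of the preferred change is one sentence in each of two places and no extra data. With equal SDs, power (100,000 simulations) falls from 96.7% to 96.3% with 60 controls and from 97.7% to 97.1% with 80 at a 1 SD difference. At 0.5 SD it falls from 48.5% to 47.2% and from 50.7% to 48.8%.
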